### **5.2.11. Adequate post-baseline tumor assessment**

An adequate post-baseline assessment is defined as an assessment where a response of CR, PR, SD, non-CR/non-PD, or PD can be determined (see Section 6.1.1.1). Time points where the response is not evaluable (NE) or no assessment was performed will not be used for determining the censoring date.

## **5.3. Methods to Manage Missing Data**

### **5.3.1. Missing data**

Unless otherwise specified, all data will be evaluated as observed, and no imputation method for missing values will be used.

In all patient data listings imputed values will be presented. In all listings imputed information will be flagged.

Missing statistics, eg when they cannot be calculated, should be presented as 'ND' or 'NA'. For example, if N=1, the measure of variability (SD) cannot be computed and should be presented as 'ND' or 'NA'.

#### **5.3.1.1. Pharmacokinetic concentrations**

##### **Concentrations Below the Limit of Quantification**

For all calculations, figures and estimation of individual pharmacokinetic parameters, all concentrations assayed as below the level of quantification (BLQ) will be set to zero. In log-linear plots these values will not be represented. The BLQ values will be excluded from calculations of geometric means and their CIs. A statement similar to 'All values reported as BLQ have been replaced with zero' should be included as a footnote to the appropriate tables and figures.

##### **Deviations, Missing Concentrations and Anomalous Values**

In summary tables and plots of median profiles, concentrations will be set to missing if one of the following cases is true:

1. A concentration has been reported as ND (ie, not done) or NS (ie, no sample);
2. A deviation in sampling time is of sufficient concern or a concentration has been flagged as anomalous by the clinical pharmacologist.

Summary statistics will not be presented at a particular time point if more than 50% of the data are missing. For analysis of pharmacokinetic concentrations, no values will be imputed for missing data.

### **5.3.1.2. Pharmacokinetic parameters**

Whether actual or nominal PK sampling time will be used for the derivation of PK parameters will be determined by the results of interim PK analyses. If a PK parameter is missing, the parameter will be coded as NC (ie, not calculated). NC values will not be generated beyond the day that a patient discontinues.

In summary tables, statistics will be calculated by setting NC values to missing. Statistics will not be presented for a particular treatment if more than 50% of the data are NC. For statistical analyses (ie, analysis of variance), PK parameters coded as NC will also be set to missing.

If an individual patient has a known biased estimate of a PK parameter (due for example to a deviation from the assigned dose level), this will be footnoted in summary tables and will not be included in the calculation of summary statistics or statistical analyses.

### **5.3.2. Handling of incomplete dates**

#### **5.3.2.1. Disease history**

Incomplete dates for disease history (eg, initial diagnosis date, date of documented, locally advanced, inoperable or metastatic disease diagnosis, date of response or progression in prior treatment) will be imputed as follows:

- If the day is missing, it will be imputed to the 15th day of the month.
- If both day and month are missing and the year is prior to the year of the first study treatment, the month and day will be imputed as July 1st.
- If both day and month are missing and the year is same as the year of the first study treatment, the month and day will be imputed as January 1st.
- If the date is completely missing, no imputation will be performed.

#### **5.3.2.2. Adverse events**

Incomplete AE-related dates will be imputed as follows:

- If the AE onset date is missing completely, then the onset date will be replaced by the start of study treatment.
- If only the day part of the AE onset date is missing, but the month and year are equal to the start of study treatment, then the AE onset date will be replaced by the start of study treatment. For example, if the AE onset date is --/JAN/2015, and study treatment start date is 15/JAN/2015, then the imputed AE onset date will be 15/JAN/2015.
- If both the day and month of the AE onset date are missing but the onset year is equal to the start of study treatment, then the onset date will be replaced by the start of study

treatment. For example, if AE onset date is --/---/2014, and study treatment start date is 19/NOV/2014, then the imputed AE onset date will be 19/NOV/2014.

- In all other cases the missing onset day or missing onset month will be replaced by 1.
- Incomplete stop date will be replaced by the last day of the month (if day is missing only), if not resulting in a date later than the date of patient's death. In the latter case the date of death will be used to impute the incomplete stop date.
- In all other cases the incomplete stop date will not be imputed. If stop date of AE is after the date of cut-off outcome of AE is ongoing at cut-off.

### **5.3.2.3. Prior and concomitant medications**

Incomplete prior/concomitant medication dates will be imputed as follows:

- If the medication date is missing completely, then the medication date will be replaced by the start of study treatment.
- If the day of medication date is missing, but the month and year are equal to the start of study treatment, then the medication date will be replaced by the start of study treatment. For example, if the medication start date is --/JAN/2015, and study treatment start date is 15/JAN/2015, then the imputed medication start date will be 15/JAN/2015.
- If both the day and month of medication start date are missing but the start year is equal to the start of study treatment, then the medication date will be replaced by the start of study treatment. For example, if the medication start date is --/---/2014, and study treatment start date is 19/NOV/2014, then the imputed medication start date will be 19/NOV/2014.
- In all other cases the missing medication day or missing medication month will be replaced by 1.
- Incomplete stop date will be replaced by the last day of the month (if day is missing only), if not resulting in a date later than the date of patient's death. In the latter case the date of death will be used to impute the incomplete stop date.
- In all other cases the incomplete medication stop date will not be imputed.

### **5.3.2.4. Exposure**

No imputation will be done for first dose date. Date of last dose of study drug, if unknown or partially unknown, will be imputed as follows:

- If the last date of study drug is completely missing and there is no End of Treatment eCRF page and no death date, the patient should be considered to be ongoing and use the cut-off date for the analysis as the last dosing date
- If the last date of study drug is completely or partially missing and there is EITHER an End of Treatment eCRF page OR a death date available (within the cut-off date), then imputed last dose date is:  
= 31DECYYYY, if only Year is available and Year < Year of min (EOT date, death date)

- = Last day of the month, if both Year and Month are available and Year = Year of min (EOT date, death date) and Month < the month of min (EOT date, death date)
- = min (EOT date, death date), for all other cases.

### 5.3.3. Imputation rules for date of last contact and efficacy assessments

#### 5.3.3.1. Date of last contact

The date of last contact will be derived for patients not known to have died at the analysis cut-off using the latest complete date among the following:

- All patient assessment dates (blood draws (laboratory, PK), vital signs, performance status, ECG, tumor assessments)
- Start and end dates of anti-cancer therapies administered after study treatment discontinuation
- AE start and end dates
- Last date of contact collected on the 'Survival Follow-up' eCRF (do not use date of survival follow-up assessment unless status is 'alive')
- Study drug start and end dates
- Withdrawal of consent date
- Date of discontinuation on disposition eCRF pages (do not use if reason for discontinuation is lost to follow-up).

Only dates associated with actual examinations of the patient will be used in the derivation. Dates associated with a technical operation unrelated to patient status such as the date a blood sample was processed will not be used. Assessment dates after the cut-off date will not be applied to derive the last contact date.

#### 5.3.3.2. Death date

Missing or partial death dates will be imputed based on the last contact date:

- If the date is missing it will be imputed as the day after the date of last contact
- If the day or both day and month is missing, death will be imputed to the maximum of the full (non-imputed) day after the date of last contact and the following:
  - Missing day: 1st day of the month and year of death
  - Missing day and month: January 1st of the year of death

#### 5.3.3.3. Tumor assessments

All investigation dates (eg, X-ray, CT scan) must be completed with day, month and year.

If there are multiple scan dates associated with an evaluation, ie, radiological assessments occur over a series of days rather than the same day, the choice of date of assessment could impact the date of progression and/or date of response. If there are multiple scan dates

associated with an evaluation, the earliest of the scan dates associated with the evaluation will be used as the date of assessment.

If one or more investigation dates for an evaluation are incomplete but other investigation dates are available, the incomplete date(s) are not considered for calculation of the assessment date and assessment date is calculated as the earliest of all investigation dates (eg, X-ray, CT-scan).

If all measurement dates for an evaluation have no day recorded, the 1st of the month is used.

If the month is not completed, for any of the investigations for an evaluation, the respective assessment will be considered to be at the date which is exactly between the previous and the following assessment. If both a previous and following assessments are not available, this assessment will not be used for any calculations.

#### **5.3.3.4. Date of start of new anti-cancer therapy**

Incomplete dates for start date of new anti-cancer therapy (drug therapy, radiation, surgery) will be imputed as follows and will be used for determining censoring dates for efficacy analyses and in the derivation of the end of on-treatment period. PD date below refers to PD date by investigator assessment.

- The end date of new anti-cancer therapy will be included in the imputations for start date of new anti-cancer therapy. If the end date of new anti-cancer therapy is
  - completely missing then it will be ignored in the imputations below
  - partially missing with only year (YYYY) available then the imputations below will consider 31DECYYYY as the end date of the new anti-cancer therapy
  - partially missing with only month and year available then the imputations below will consider the last day of the month for MMMYYYY as the end date of the new anti-cancer therapy
- For patients who have not discontinued study treatment at the analysis cut-off date, last dose of study treatment is set to the analysis cut-off date in the imputations below.
- If the start date of new anti-cancer therapy is completely or partially missing, then the imputed start date of new anti-cancer therapy is derived as follows:
  - Start date of new anti-cancer therapy is completely missing  
Imputed start date = min [max (PD date + 1, last dose of study treatment + 1), end date of new anti-cancer therapy]
  - Only year (YYYY) for start of anti-cancer therapy is available  
IF YYYY < Year of min [max (PD date + 1, last dose of study treatment + 1), end date of new anti-cancer therapy] THEN imputed start date = 31DECYYYY;  
ELSE IF YYYY = Year of min [max (PD date + 1, last dose of study treatment + 1), end date of new anti-cancer therapy]

THEN imputed start date = min [max (PD date + 1, last dose of study treatment + 1), end date of new anti-cancer therapy]

ELSE IF YYYY > Year of min [max (PD date + 1, last dose of study treatment + 1), end date of new anti-cancer therapy]

THEN imputed start date = 01JANYYYY

- Both Year (YYYY) and Month (MMM) for start of anti-cancer therapy are available  
IF  
    YYYY = Year of min [max (PD date + 1, last dose of study treatment + 1), end date of new anti-cancer therapy], AND  
    MMM < Month of min [max (PD date + 1 day, last dose of study treatment + 1 day), end date of new anti-cancer therapy]  
THEN  
    imputed start date = DAY (Last day of MMM) MMM YYYY;  
ELSE IF  
    YYYY = Year of min [max (PD date + 1, last dose of study treatment + 1), end date of new anti-cancer therapy], AND  
    MMM = Month of min [max (PD date + 1 day, last dose of study treatment + 1 day), end date of new anti-cancer therapy]  
THEN  
    imputed start date = min [max (PD date + 1 day, last dose of study treatment + 1 day), end date of new anti-cancer therapy]);  
ELSE IF  
    YYYY = Year of min [max (PD date + 1, last dose of study treatment + 1), end date of new anti-cancer therapy], AND  
    MMM > Month of min [max (PD date + 1 day, last dose of study treatment + 1 day), end date of new anti-cancer therapy]  
THEN  
    imputed start date = 01 MMM YYYY;  
ELSE IF  
    YYYY < Year of min [max (PD date + 1, last dose of study treatment + 1), end date of new anti-cancer therapy]  
THEN  
    imputed start date = DAY (Last day of MMM) MMM YYYY;  
ELSE IF  
    YYYY > Year of min [max (PD date + 1, last dose of study treatment + 1), end date of new anti-cancer therapy]

THEN

imputed start date = 01 MMM YYYY.

## 6. ANALYSES AND SUMMARIES

Refer to Section 4 for definitions of analysis sets and Section 5.2 for general methodology.

### 6.1. Primary Endpoint

#### 6.1.1. Objective response as assessed by the Investigator per RECIST v1.1

##### 6.1.1.1. Primary analysis

The following analyses will be based on the FAS by treatment group. Assessment of response will be made using RECIST v1.1. Assessments below refer to investigator assessment.

**Best overall response (BOR)** will be assessed based on reported overall lesion responses at different evaluation time points from the date of first dose of study treatment until the first documentation of PD, according to the following rules. Only tumor assessments performed on or before the start date of any further anti-cancer therapies will be considered in the assessment of BOR. Clinical deterioration will not be considered as documentation of disease progression.

##### **BOR Based on Confirmed Responses:**

- CR = at least two determinations of CR at least 4 weeks apart and before first documentation of PD
- PR = at least two determinations of PR or better (PR followed by PR or PR followed by CR) at least 4 weeks apart and before first documentation of PD (and not qualifying for a CR)
- SD (applicable only to patients with measurable disease at baseline) = at least one SD assessment (or better)  $\geq$  6 weeks after the date of first dose of study treatment and before first documentation of PD (and not qualifying for CR or PR).
- Non-CR/non-PD (applicable only to patients with non-measurable disease at baseline) = at least one non-CR/non-PD assessment (or better)  $\geq$  6 weeks after the date of first dose of study treatment and before first documentation of PD (and not qualifying for CR or PR).
- PD = first documentation of PD  $\leq$  12 weeks after the date of first dose of study treatment (and not qualifying for CR, PR, SD or non-CR/non-PD).
- NE: all other cases.

An objective status of PR or SD cannot follow one of CR. SD can follow PR only in the rare case that tumor increases by less than 20% from the nadir, but enough that a previously documented 30% decrease from baseline no longer holds. If this occurs, the sequence PR-

SD-PR is considered a confirmed PR. A sequence of PR – SD – SD – PD would be a best response of SD if the window for SD definition has been met.

**Objective Response (OR)** is defined as confirmed BOR of CR or PR according to RECIST v1.1.

Patients who do not have a post-baseline radiographic tumor assessment due to early progression, who receive anti-cancer therapies other than the study treatments prior to reaching a CR or PR, or who die, progress, or drop out for any reason prior to reaching a CR or PR will be counted as non-responders in the assessment of OR. Each patient will have an objective response status (0: no OR; 1: OR). OR rate (ORR) is the proportion of patients with OR in the analysis set.

ORR by treatment group will also be calculated along with the 2-sided 95% CI using the Clopper-Pearson method  (exact CI for a binomial proportion as computed by default by the FREQ procedure using the EXACT option).

In addition, the frequency (number and percentage) of patients with a confirmed BOR of CR, PR, SD, non-CR/non-PD (applicable only to patients with non-measurable disease at baseline), PD, and NE will be tabulated. Patients with confirmed BOR of NE will be summarized by reason for having NE status. The following reasons will be used:

- No baseline assessment
- No post-baseline assessments due to death (i.e., death prior to 8 weeks after first dose of study treatment)
- No post-baseline assessments due to other reasons
- All post-baseline assessments have overall response NE
- New anti-cancer therapy started before first post-baseline assessment
- SD of insufficient duration (<6 weeks after the date of first dose of study treatment without further evaluable tumor assessments)
- PD too late (>12 weeks after the date of first dose of study treatment)

Special and rare cases where BOR is NE due to both SD of insufficient duration and late PD will be classified as ‘SD too early’ (ie, SD of insufficient duration).

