#### **6.2.2.4. Progression-free survival**

Progression-free survival (PFS) is defined as the time from the date of first dose of study treatment to the date of the first documentation of PD or death due to any cause, whichever occurs first.

PFS data will be censored on the date of the last adequate tumor assessment for patients who do not have an event (PD or death), for patients who start a new anti-cancer therapy prior to an event (see Section 5.2.6) or for patients with an event after 2 or more missing tumor assessments. Patients who do not have an adequate baseline tumor assessment or who do not have an adequate post-baseline tumor assessment will be censored on the date of first dose of study treatment unless death occurred on or before the time of the second planned tumor assessment (ie  $\leq$  16 weeks after the date of first dose of study treatment) in which case the death will be considered an event.

In this study antitumor activity will be assessed through radiological tumor assessments conducted at screening and every 8 weeks ( $\pm$  7 days) for 1 year from start of study treatment, and then every 12 weeks ( $\pm$  7 days) thereafter until PD regardless of discontinuation of study treatment or initiation of subsequent anti-cancer therapy.

The censoring and event date options to be considered for the PFS analysis are presented in Table 7.

PFS (months) = [date of event or censoring – date of first dose of study treatment +1]/30.4375

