**Table 7. Outcome and Event Dates for PFS Analyses**

Scenario	Date of event/censoring	Outcome
No adequate baseline assessment	Date of first dose of study treatment a	Censored a
PD or death	Date of PD or death	Event
- After at most one missing or inadequate post-baseline tumor assessment, OR - $\leq 16$ weeks after the date of first dose of study treatment		
PD or death	Date of last adequate tumor assessment b documenting no PD before new anti-cancer therapy is given or missed tumor assessments	Censored
No PD and no death	Date of last adequate tumor assessment b documenting no PD before new anti-cancer therapy is given or missed tumor assessments	Censored
Treatment discontinuation due to 'Disease progression' without documented progression	Not applicable	Information is ignored. Outcome is derived based on documented progression only.
New anti-cancer therapy given	Date of last adequate tumor assessment b documenting no PD before new anti-cancer therapy is given or missed tumor assessments	Censored

a However if the patient dies  $\leq 16$  weeks after the date of first dose of study treatment the death is an event with date on death date

b If there are no adequate post-baseline assessments prior to PD or death, then the time without adequate assessment should be measured from the date of first dose of study treatment; if the criteria were met the censoring will be on the date of first dose of study treatment

Kaplan-Meier estimates (product-limit estimates) will be presented by treatment group together with a summary of associated statistics including the median PFS time with 2-sided 95% CIs. In particular, the PFS rates at 2, 4, 6, 8, 10, 12, 15, 18, and 24 months will be estimated with corresponding 2-sided 95% CIs. The CIs for the median will be calculated according to Brookmeyer and Crowley (1982) and the CIs for the survival function estimates at the time points defined above will be derived using the log-log transformation according to Kalbfleisch and Prentice (2002) (confittype=loglog default option in SAS Proc LIFETEST) with back transformation to a CI on the untransformed scale. The estimate of the standard error will be computed using Greenwood's formula.

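### The 12-week limit on PD as best overall response falls between scans 1 and 2, so PD first shown at scan 2 after a missing or NE scan 1 is tabulated as not evaluable while PFS counts it as an event

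*SAP*

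**What the plan says.** SAP section 6.1.1.1 assigns each patient one BOR category. PD is accepted only if first documented no later than "12 weeks after the date of first dose of study treatment (and not qualifying for CR, PR, SD or non-CR/non-PD"). Cases that fit no category are NE and are broken down by reason. One listed reason is "PD too late (>12 weeks after the date of first dose of study treatment"). A further sentence deals with cases "where BOR is NE due to both SD of insufficient duration and late PD". The section also says: "Only tumor assessments performed on or before the start date of any further anti-cancer therapies will be considered in the assessment of BOR".

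The scan schedule is in SAP section 6.2.2.4: "In this study antitumor activity will be assessed through radiological tumor assessments conducted at screening and every 8 weeks", with 7 days either side, for the first year. The same section sets a 16-week cut-off for deaths without adequate tumor assessments, described as whether "death occurred on or before the time of the second planned tumor assessment". Protocol section 7.6 gives the same 8-week interval and adds scans whenever PD is suspected.

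For PFS, SAP Table 7 counts PD as an event on its date under either of two conditions. The first is "After at most one missing or inadequate post-baseline tumor assessment, OR"; the second is PD or death within 16 weeks of first dose. SAP section 5.2.11 treats a post-baseline scan as adequate if "a response of CR, PR, SD, non-CR/non-PD, or PD can be determined".

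Protocol Appendix 4 defines BOR as the best response recorded from the start of treatment until progression. It puts no time limit on PD.

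**The concern.** The 12-week limit corresponds to no scheduled scan. Other time limits in the same analyses follow the 8-week schedule: the early-death reason for NE uses 8 weeks, and the PFS and DR tables use 16. A patient who misses scan 1, or whose scan 1 is NE, cannot have BOR of PD on the basis of a scan 2 done on time.

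The same investigator reading is then reported in two ways. The PFS table shows a documented progression, and the BOR table shows a patient who could not be evaluated. What is at stake is the PD and NE percentages in a prespecified descriptive table, not the primary estimate.

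**Working it through.** **Inputs.** The BOR limit for PD is 12 weeks (SAP 6.1.1.1). The scan interval is 8 weeks, plus or minus 7 days (SAP 6.2.2.4). The PFS event rule is in SAP Table 7. The planned cohort size is 40 (SAP 5.1.1). Days below are elapsed days after first dose; the SAP's study-day numbering adds one to every figure and leaves the comparisons unchanged.

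**The plan's own figure.** The second planned scan is at 2 x 8 = 16 weeks, or 16 x 7 = 112 days. This agrees with the 16 weeks stated in SAP 6.2.2.4.

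**Windows.** Scan k falls on day 56k, plus or minus 7. The limit is 12 x 7 = 84 days.

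| Scan | Window (days) | In-window days at or before day 84 |
|---|---|---|
| 1 | 49-63 | 15 of 15 |
| 2 | 105-119 | 0 of 15 |
| 3 | 161-175 | 0 of 15 |

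Day 84 is 84 - 63 = 21 days after the scan 1 window closes and 105 - 84 = 21 days before the scan 2 window opens. The result does not depend on the 7-day window. With 3 days either side, scan 2 is days 109-115 and 0 of 7 days qualify. With no window it is day 112, which also fails.

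**Both rule sets applied to the same scans.** These cases assume an adequate baseline, no new anti-cancer therapy before the PD scan, and no other evaluable scan.

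| Scan 1 | Later finding | BOR | PFS |
|---|---|---|---|
| PD | - | PD | Event |
| SD | PD at scan 2 | SD | Event |
| Missing or NE | PD on day 105, 112 or 119 | NE | Event |
| Missing | Scan 2 missing, PD at week 24 | NE | Censored at first dose |

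The conflict is in the third row, where exactly one scan is missing or NE. On days 105-112 (8 of 15) both Table 7 conditions for an event are met. On days 113-119 (7 of 15) only the at-most-one-missing condition is met, and that is sufficient.

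**Alternative limits.** A 16-week limit (day 112) covers 8 of the 15 scan 2 days. A 17-week limit (day 119) covers 15 of 15 and no scan 3 day, since scan 3 opens 161 - 119 = 42 days later.

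**Size.** One patient is 1/40 = 2.5 percentage points moved from PD to NE; two are 5.0 points. The documents give no rate for this pattern. As an assumption only, rates of 2%, 5% and 10% would give 0.8, 2 and 4 patients per 40. The change in ORR is 0 in every case.

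**The case against.** The strongest defense is that NE is the right answer. With scan 1 missing, the week-8 status is unknown. Had it been SD, BOR would have been SD. PD at scan 2 alone cannot separate a patient who was never controlled from one who was stable and then progressed. BOR and PFS ask different questions, and the SAP already lets NE sit beside a PFS event: a patient who dies before week 8 without a scan is NE for BOR and an event for PFS. A limit midway between two scans also separates a late scan 1 cleanly from scan 2.

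The SAP does not apply that reasoning. A patient who misses scan 1 and shows PD on an unscheduled scan by day 84 has BOR of PD, although the week-8 status is just as unknown. Appendix 4 defines BOR by what was recorded, and here the only recorded response is PD. The early-death case is not parallel, because death is not a RECIST response category.

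Several parts of the objection stand:

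- The rule is explicit, and affected patients can be traced through the late-PD row and the protocol section 9.3.2 listing of progression date with BOR and PFS.
- Section 5.2.11 serves to set censoring dates and does not assign BOR categories.
- Appendix 4 is silent on when PD becomes NE, and the SAP may modify the protocol's plans, so there is no direct contradiction there.
- The SAP's version history is redacted, so the absence of a visible reason for 12 weeks proves nothing.
- Scans for suspected PD will rescue some patients, and the number affected may be zero.

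**Conclusion.** The concern holds and is minor. For a patient with an adequate baseline, no earlier new anti-cancer therapy, scan 1 missing or NE, and no evaluable scan before scan 2, PD at an in-window scan 2 always gives BOR of NE and always counts as a PFS event.

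ORR, its exact confidence interval and the time-to-event analyses are unaffected. The consequence is an inconsistency between two prespecified tables, with a documented progressor placed under NE. Its total size depends on a patient count that the documents do not supply.

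**What to change.** In SAP section 6.1.1.1, change the PD limit to no more than 17 weeks (119 days) after first dose, and change the matching NE reason to PD after 17 weeks. The sentence on cases with both early SD and late PD then applies only to PD after 17 weeks.

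Keep a limit. Without one, PD at scan 3 after two missed scans would become BOR of PD while Table 7 censors PFS. With 17 weeks that patient stays NE and censored, so the two tables agree there as well.

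The cost is two numbers in the text and one constant in the BOR program. A few patients may move from NE to PD. The definition and analysis of objective response do not change, so this is not the major modification of the primary endpoint for which SAP section 2 requires a protocol amendment. One gap remains: a scan 2 done after day 119 would still give NE, while PFS could still count it as an event.

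If the sponsor prefers to keep 12 weeks, the SAP should at least give the reason and footnote the affected patients in the BOR table.
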